7.7 EXTENT OF EXPOSURE

Exposure to study drug will be presented on the TS using actual maintenance treatment.

A descriptive summary and frequency table will be produced of the extent of exposure, as defined in [Section 5.4.3](#). The total patient-years exposure will also be summarised; the 28-day REP after the last dose of study treatment (see [Section 6.1.6](#)) will not be included for this purpose.

A frequency table will be produced of duration on study (regardless of whether the patient remained on-treatment) using the same categories as extent of exposure, to provide a simple assessment of the extent to which patients who discontinued treatment early were successful in being retained in the study.

7.8 SAFETY ANALYSIS

All safety analyses will be performed on the TS, using actual maintenance treatment, and including only on-treatment data (unless otherwise specified in [Section 7.8.1](#)), regardless of whether early treatment discontinuation was COVID-19 related.

Selected AE summaries will also be presented on the TS using planned maintenance treatment. Where this is also planned, it is clearly specified.

7.8.1 Adverse Events

The analyses of adverse events will be descriptive in nature. All analyses of AEs will be based on the number of patients with AEs and not on the number of AEs.

The analysis of adverse events will be based on the concept of treatment emergent adverse events. AEs will be considered “on-treatment” if the AE start date meets the 28-day REP criterion (see [Section 6.1.6](#)). AEs occurring prior to the start of treatment will be assigned to “screening”. AEs occurring more than 28 days after the last dose of study treatment will be assigned to “follow-up”. Unless otherwise specified, on-treatment AEs will be pooled across dose escalation and maintenance periods. It should also be noted that the protocol encourages continued study participation for patients who have discontinued treatment early. It is therefore expected that for some patients there will be off-treatment data captured during the planned treatment period, which will make the “follow-up” period included in AE summaries longer than the 4-week definition of scheduled “follow-up” used in the protocol, perhaps in some cases considerably longer than this.

An overall summary of adverse events will be presented for all treated patients. This summary will show the number and percent of patients with any AE, any investigator defined drug-related AE, any AE leading to the discontinuation of study medication, any AESI (as determined by the investigator), any serious AE (including reason for serious (death, life-threatening, disability/permanent damage, required or prolonged hospitalization, congenital anomaly/birth defect and other medically important events)), and any drug-related serious AE. The overall summary will be presented:

- Using actual maintenance treatment, with the treatment period pooled across, and split into, dose escalation and maintenance periods, respectively.
- Using planned maintenance treatment, with the treatment period pooled across dose escalation and maintenance periods only.

AEs will be coded using the version of the MedDRA coding dictionary in force at final DBL. The frequency of patients with all AEs will be summarised by treatment, primary system organ class (SOC) and preferred term (PT). A patient with multiple on-treatment occurrences of the same preferred term meeting the criteria for inclusion in the table will be counted only once in these tabulations. SOC's will be sorted by descending overall frequency; PT's will be sorted by descending overall frequency (within SOC). The summary of all AEs will be presented:

- Using actual maintenance treatment, with the treatment period pooled across, and split into, dose escalation and maintenance periods, respectively.

- Using planned maintenance treatment, with the treatment period pooled across dose escalation and maintenance periods only.

The AE summary by primary SOC and PT will also be repeated for each of the following, using actual maintenance treatment with the treatment period pooled across dose escalation and maintenance periods, only:

- AEs leading to treatment discontinuation
- Serious AEs
- Investigator-defined drug-related AEs
- Drug-related serious AEs.

An additional table will present the frequency of patients with AEs by worst intensity (mild, moderate, severe) and by primary SOC and PT. Where no events meet the criteria for inclusion in one of these tables, the table will be shown as indicating no events of that intensity have occurred.

The following tables will be produced by baseline body weight subgroup (< 100 / ≥ 100 kg):

- Overall AE summary
- Summary of all AEs by primary SOC and PT
- Summary of AEs leading to treatment discontinuation by primary SOC and PT.

For disclosure of AE data on ClinicalTrials.gov, the frequency of patients with non-serious AEs occurring with an incidence of greater than 5% (PT occurring in more than 5% of treated patients in one or more treatment groups) will be summarised by treatment, primary SOC and PT. The frequency of patients with serious AEs and drug related serious AEs will also be summarised respectively.

For disclosure of AE data in the EudraCT register, the frequency of patients with AEs, the frequency of patients with non-serious AEs with an incidence of greater than 5% (as above) and the frequency of patients with serious AEs will be summarised. Furthermore, the total number of treated patients by country and by age group will be summarised.

An exposure-adjusted summary of all AEs by primary SOC and PT will also be produced. For this purpose, the time at risk will be defined for specific AEs as follows:

- For patients with no events, the time at risk is the number of days on-treatment (inclusive), as defined in [Section 6.1.6](#)
- For patients with one or more event, the time at risk is the number of days from the start of treatment to the start of the first on-treatment event (inclusive).

The total time at risk (years) for a treatment group is the sum of the individual patient times at risk for that treatment group (days) divided by 365.25. Multiple occurrences of the same event for a particular patient will not be counted as separate events in this summary; a patient will either be considered to have no events of the type being summarised, or to have one or more occurrences of that event.

Additional trial-specific information captured in the eCRF for acute gall bladder disease, acute pancreatitis and thyroid mass will be listed only and not summarised.

A frequency table will be produced of symptoms of injection site reaction (swelling, induration, heat, redness, pain, other) for the subset of patients with the event.

AESIs

Hepatic injury is the only AESI pre-specified in the CTP. No further AESIs have been identified through increasing knowledge of the drug safety profile during the conduct of the trial.

AESIs as recorded by the investigator on the eCRF page will be summarised as part of the overall AE summary, described above.

Investigator-recorded AESIs will also be summarised by treatment, primary SOC and PT.

An additional table will present the frequency of patients with AEs possibly indicating hepatic injury as defined by the four MedDRA subSMQ definitions given below:

- Liver related investigations, signs and symptoms (narrow subSMQ)
- Cholestasis and jaundice of hepatic origin (narrow subSMQ)
- Hepatitis, non-infectious (narrow subSMQ)
- Hepatic failure, fibrosis and cirrhosis and other liver damage-related conditions (narrow subSMQ).

This table will be summarised by treatment, MedDRA subSMQ, primary system organ class and preferred term. Any preferred term which is classified under more than one subSMQ will be included under each relevant subSMQ.

Adjudicated Events

The number and percent of patients with each of the following confirmed adjudicated events (as defined in the CTP) will be presented:

- All-cause death
- Cardiovascular event
- Cerebrovascular disease
- Heart failure requiring hospitalization
- Pancreatitis
- Neoplasm
- Thyroid mass requiring surgery.

7.8.2 Laboratory data

The analyses of laboratory data will be descriptive in nature and will be based on BI standards. Central laboratory data will be used for all displays described below, unless otherwise specified. Summaries of eGFR and UACR will be included as part of the routine summaries of laboratory variables.

For continuous safety laboratory variables where reference ranges exist, normalised values will be derived (i.e. transformation to both a standard unit and to a standard reference range). Descriptive statistics will be presented over time for absolute values and changes from baseline in each of the laboratory variables where normalised values are possible. All scheduled weeks will be presented as well as last value, minimum value and maximum value on-treatment.

For continuous safety laboratory variables where reference ranges exist, a shift table will be produced summarising the shifts from baseline to the last value on treatment, and displaying categories “Low”, “Normal” and “High” with respect to the relevant reference range. Standardised values (i.e. transformation to a standard unit only) will be used for this purpose.

For categorical safety laboratory variables, a shift table will be produced summarising the shifts from baseline to the last value on treatment, and displaying each relevant category. For any semi-quantitative variables (i.e. those recorded as either “Normal” or with a continuous numerical value otherwise), the shift table will display categories “Normal” and “Abnormal” only, without further categorisation of the continuous values into different degrees of abnormality.

Potentially clinically significant abnormalities will be identified using BI standard rules. A listing containing these rules (including for each variable whether a low range applies, or a high range applies, or both) will be included in the CTR. A frequency table will be used to summarise the number and percentage of patients with potentially clinically significant abnormalities, for each variable where a BI standard rule exists. Patients with an abnormal value at baseline will be presented separately on this table.

A separate listing will present potentially clinically significant abnormal lab values; for each functional lab group all patient’s laboratory values will be listed, if there exists at least one value with clinically significant abnormality within the group.

The following additional investigations will be made for elevated liver enzymes:

A frequency table will be produced of the following categories. A patient will be included in each relevant category, defined using the maximum post-baseline ALT and AST values observed on-treatment ([Section 6.1.6](#)), regardless of the baseline AST and ALT values:

- ALT or AST $\geq 3 \times$ ULN
- ALT or AST $\geq 5 \times$ ULN
- ALT or AST $\geq 8 \times$ ULN
- ALT or AST $\geq 10 \times$ ULN
- ALT or AST $\geq 20 \times$ ULN
- ALT or AST $\geq 3 \times$ ULN with total bilirubin $\geq 2 \times$ ULN.

In the above categories, each occurrence within a patient of a post-baseline elevation ALT or AST $\geq 3 \times$ ULN will be used as a trigger for the determination of the elevation of total elevation of bilirubin $\geq 2 \times$ ULN. The proposed time interval for the follow-up of total bilirubin is 30 days after the occurrence of the post-baseline ALT or AST elevation.

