6.2.2 Treatment period(s)

Before visit 2, patients will have to record their food intake in a 3-days food diary (see [section 5.1.5](#)).

Patients who meet all the protocol criteria will be randomized at visit 2. After randomization, patients will start the treatment period which includes a dose escalation phase, followed by the dose maintenance phase as shown in [Figure 3.1: 1](#).

Procedures to be completed at each visit can be found in the Flow Chart.

At visits specified in the Flow Chart, patients should be instructed to come in the fasting state after at least 10 hours without food intake. Water intake is allowed. On days when fasting is required, the clinic visit should ideally be scheduled in the mornings, if this is convenient for the patient.

During visits, vital signs must be measured before blood sampling.
Drug injection should always take place after all assessments of the visit are done.

At each visit, patients should be advised to follow the recommended diet and exercise plan and to record their compliance daily on the provided diary. Diet and exercise counselling sessions are held at visits indicated in the [Flow Chart](#). When necessary from a logistic point of view it is possible to have the diet/exercise counselling on a different day than the actual dosing visit, but within the timewindow of the visit.

Unscheduled visits may be arranged if necessary. Procedures completed during an unscheduled visit will depend on the circumstances under which the visit was scheduled, and at the discretion of the investigator.

Exceptionally, and after consultation with sponsor, one visit could be completed a few days in advance to accommodate for patient's imperatives. The call to IVRS and drug allocation would be made, but the injection would occur as per the initial schedule and allowed time-window.

After completion of the treatment period, patients will have the End of Treatment visit, one week after last drug injection. All patients will then enter the follow-up period and complete the observation period with the follow-up visit which has to be set at least 4 weeks after last drug injection.

If a patient discontinues drug during the treatment period (dose escalation phase, or maintenance phase), the patient will undergo the procedures of "end of treatment" visit, ideally 7 days after the last drug injection.

Safety lab, other laboratory tests during the treatment period (from V3 to visit 17) :

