If blood sampling for central lab at the trial site is not possible, safety lab analyses can be performed at a local lab. The results of the lab tests must be transferred to the investigator who ensures medical review and proper documentation in the eCRF.

Minimum required safety lab parameters are

Haematology: Haematocrit, Hemoglobin, Red Blood Cells / Erythrocytes, White blood cells / Leukocytes, Platelet Count / Thrombocytes

Clinical chemistry: ALT (alanine aminotransaminase, SGPT), AST (aspartate aminotransaminase, SGOT), Bilirubin total, Amylase, Lipase

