| 
Rationale for change
 | 
Give flexibility
 |
| 
Section to be changed
 | 
6.2.2 treatment period
 |
| 
Description of change
 | 
The following text was added :
 
Safety lab, other laboratory tests during the treatment period (from V3 to visit 17) : If blood sampling for central lab at the trial site is not possible, safety lab analyses can be performed at a local lab. The results of the lab tests must be transferred to the investigator who ensures medical review and proper documentation in the eCRF. Minimum required safety lab parameters are Haematology: Haematocrit, Hemoglobin, Red Blood Cells / Erythrocytes, White blood cells / Leukocytes, Platelet Count / Thrombocytes Clinical chemistry: ALT (alanine aminotransaminase, SGPT), AST (aspartate aminotransaminase, SGOT), Bilirubin total, Amylase, Lipase
 |
| 
Rationale for change
 | 
Due to COVID-19sanitary crisis it may happen that central lab cannot provide tubes or results
 |
| 
Section to be changed
 | 
6.2.2 treatment period
 |

| | | |
|------------------------------|--|---|
| | | 
The following text was added :
 
Exceptionally, and after consultation with sponsor, one visit could be completed a few days in advance to accommodate for patient's imperatives. The call to IVRS and drug allocation would be made, but the injection would occur as per the initial schedule and allowed time-window.
 |
| Rationale for change | | Avoid too many withdrawals due to patients missing a visit and therefore would miss 2 consecutive doses |
| Section to be changed | | 10.1 Available dosing by Combination of syringes |
| Description of change | | 
Five concentrations of BI 456906 are available, all available in syringes of 0,5 mL. The below combination of two syringes at every injection day will be used to obtain the various dosages used during the trial, in a blinded manner.
 
Was changed to
 
Five concentrations of BI 456906 are available, all available in syringes of 0,5 mL. The below combination of two syringes at every injection day will be used to obtain the various dosages used during the trial, in a blinded manner.
 
Exceptionnally, and when possible, a different combination may be used to avoid missing supplies
 |
| Rationale for change | | Give flexibility to the IRT system |
| Section to be changed | | 10.2 Blood pressure measurement procedures |

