7. PLANNED ANALYSIS

Descriptive statistics for continuous variables will generally be N (number of patients with non-missing values), arithmetic mean, standard deviation (SD), minimum, Q1 (lower quartile), median, Q3 (upper quartile) and maximum. In general, means, medians, other quartiles and SDs will be presented to one more decimal place than the raw data. Minimums and maximums will be presented to the same number of decimal places as the raw data.

For BI 456906 plasma concentrations, CV (arithmetic coefficient of variation), gMean (geometric mean) and gCV (geometric coefficient of variation) will also be presented. The data format for descriptive statistics of concentrations will be identical with the data format of the respective concentrations.

Tabulations of frequencies for categorical data will include all possible non-missing categories unless otherwise specified (e.g. AE terms), and will display the number of patients in a category as well as the percentage (%) relative to the respective treatment group. Percentages will be rounded to one decimal place. A missing category will be displayed only if there are actually missing values. Percentages will be based on all patients in the respective patient set whether they have non-missing values or not.

Disposition

The disposition of patients will be displayed. This table will present the number of patients enrolled, randomised and treated. The number treated will be further presented separating the dose escalation and maintenance periods. Planned maintenance treatment (see [Section 6.1.2](#)) will be used for this table.

The number of patients who completed or who prematurely discontinued study treatment will be summarised, along with the categorization of the primary reason for treatment discontinuation. The number of patients and reasons for prematurely discontinuing treatment will also be displayed separately for the dose escalation and maintenance periods.

The number of patients who completed or who prematurely withdrew from the study will be summarised, along with the categorization of the primary reason for study withdrawal.

Where shown on the disposition table, the percentages will be of the number of patients treated in each treatment group.

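### The liver table of ALT/AST multiples of ULN (SAP 7.8.2) uses central laboratory data only, so a patient whose only value reaching a threshold was local is not counted in that row

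*SAP*

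**What the plan says.** **Data source.** SAP 7.8.2 opens its rules on laboratory data with "Central laboratory data will be used for all displays described below, unless otherwise specified".

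**The liver table.** Later in the same section, a frequency table has six rows: ALT or AST at or above 3, 5, 8, 10 and 20 times ULN, and at or above 3 times ULN with total bilirubin at or above 2 times ULN. Patients are placed in rows "defined using the maximum post-baseline ALT and AST values observed on-treatment". For the combined row, "The proposed time interval for the follow-up of total bilirubin is 30 days after the occurrence of the post-baseline ALT or AST elevation". No data source is named for this table, so the general rule applies.

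**The local route.** Protocol 6.2.2, for Visits 3 to 17, says: "If blood sampling for central lab at the trial site is not possible, safety lab analyses can be performed at a local lab". Its minimum local panel includes ALT, AST and total bilirubin. On what happens to the values: "The results of the lab tests must be transferred to the investigator who ensures medical review and proper documentation in the eCRF". Global Amendment 2 added this text and gives as its reason that, because of COVID-19, "it may happen that central lab cannot provide tubes or results". Protocol 6.1 also asks sites to consider local laboratories when physical visits should be avoided.

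**The concern.** The protocol created a fallback so that liver monitoring could continue when the central laboratory was out of reach. The visible SAP gives the fallback results no place in the table that monitoring feeds. The values are in the eCRF, but the source rule keeps them out.

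Hepatic injury is the only AESI specified in advance, and this table is the liver display that counts transaminase rises by a numerical rule, without relying on investigator judgement. The trial also informs the phase 3 dose, with safety among the considerations (SAP 7.4.1). Counts in such tables tend to be small, so one uncounted patient can change how a row reads.

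**Working it through.** The plan gives no figure for local testing, so there is nothing to reproduce. The check is a reading of the rules, followed by an illustration of scale.

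**1. Who is affected.** The table uses the maximum on-treatment value. One central value at or above a threshold, at any on-treatment draw, is enough to count the patient. The gap is therefore limited to a patient for whom every value reaching that threshold was local. In the combined row it also covers a patient with a qualifying central ALT or AST whose only qualifying bilirubin within 30 days was local.

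**2. Does SAP 6.7 cure it?** That section says safety maxima consider every value, whether or not it was selected for a visit window. It deals with windowing and does not decide between central and local sources.

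**3. What other displays pick up.** Protocol 5.2.6.1.4 defines the AESI as ALT or AST at or above 10 times ULN, or at or above 3 times ULN with bilirubin at or above 2 times ULN in the same sample. It does not restrict the source.

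| Row | Cover if the value is local only |
|---|---|
| ≥3×, ≥5×, ≥8× ULN (3 rows) | AESI if the value is ≥10×, or has same-sample bilirubin ≥2×; otherwise only an AE that the investigator chooses to report |
| ≥10×, ≥20× ULN (2 rows) | AESI |
| ≥3× ULN with bilirubin ≥2× ULN | AESI for the same-sample case; not for a later bilirubin within the 30 days, unless ALT or AST is ≥10× |

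AESIs and the liver subSMQ table are shown by preferred term (SAP 7.8.1). They cover the event in part but do not fill the rows of this table.

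**4. Scale, on assumed inputs.** Let *s* be the share of draws done locally, assumed unrelated to having a rise, and *k* the number of a patient's draws that reach the threshold. The patient is missed if all *k* are local. That probability is *s*^*k* if draws are independent and *s* if local use is fully clustered within patients.

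| *s* (assumed) | *k* = 1 | *k* = 2, independent | *k* = 2, clustered |
|---|---|---|---|
| 2% | 2% | 0.04% | 2% |
| 5% | 5% | 0.25% | 5% |
| 10% | 10% | 1% | 10% |

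With *n* patients truly reaching the threshold, the expected number missed is at most *n* × *s*. For *n* from 2 to 10 (assumed), this runs from 2 × 0.02 = 0.04 to 10 × 0.10 = 1.0.

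**5. What one patient is worth.** With the planned 70 per group, 1/70 = 1.43 percentage points. In the 4 × 70 = 280 pooled active patients, 1/280 = 0.36 points. Safety tables use actual maintenance treatment, so real group sizes will differ.

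**6. Chance of missing anyone.** If a true rate *r* reaches the threshold, and a fraction *f* of those patients has only local qualifying values, then P(at least one missed among 280) = 1 − (1 − *rf*)^280. With *r* = 3% (assumed):
- *f* = 1%: 1 − 0.9997^280 = 8%
- *f* = 5%: 1 − 0.9985^280 = 34%
- *f* = 10%: 1 − 0.997^280 = 57%

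**The case against.** The strongest reply is that central-only is a deliberate choice. It gives one set of assays and reference ranges across about 45 sites in 13 countries, in a descriptive table with no hypothesis test. The affected group is also narrow. Safety chemistry is scheduled throughout, and local testing is for when central sampling is not possible. Protocol 5.2 encourages repeats after abnormal findings. The Week 46 or end-of-treatment draw lies outside the Visit 3 to 17 provision but within the 28-day on-treatment window. A persistent rise would usually meet a central draw. All of this stands as a limit on size. It does not help a transient rise seen only locally, because repeats are neither mandatory nor required to be central.

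Visibility is a second limit. SAP 7.9 is redacted directly after it introduces the COVID-19 impact analyses, a natural place for a local-laboratory display. SAP 5.4 and the sponsor's laboratory standards are not shown. An exception may exist there.

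Two stronger readings are tempting, and the documents support neither:
- **That a local-only rise disappears from the safety report.** Local results go through medical review by the investigator, clinically relevant findings are AEs (protocol 5.2.3), and the more severe patterns are AESIs. The loss is confined to the rows of this table.
- **That the denominator rule causes the problem.** SAP 7 says "Percentages will be based on all patients in the respective patient set whether they have non-missing values or not". A patient with other central values has an observed maximum and belongs in the denominator anyway. The rule adds something only for a patient with no central post-baseline value, and nothing shows that there is one.

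**Conclusion.** The point holds in a limited form. As visibly written, the table omits patients who reach a threshold, or have a qualifying bilirubin, on local values only. The part with least cover is a rise from 3 to below 10 times ULN without same-sample bilirubin of at least 2 times ULN, where only an investigator-reported AE remains.

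The size is unknown, because no document says how often local laboratories were used. It is probably small: at most about one patient under the assumptions shown, and far less if local use was rare. It would be larger if a site stayed on local testing over consecutive visits, or if local testing was more common in patients with rises, which the illustration assumes away. The primary analysis, type I error and power are untouched. The conclusion also assumes that no exception sits in the redacted or unseen text. This is a cheap improvement to one safety table, not an error in the trial's main analysis.

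**What to change.** In SAP 7.8.2, for the ULN-multiple liver table only:
- include eCRF-recorded local ALT, AST and total bilirubin, each divided by that laboratory's own ULN where available;
- flag these values by source, and report for each arm the number of patients who qualify on local values only;
- list any local liver value for which no ULN can be obtained.

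Keep all other laboratory displays central-only. If an exception already exists elsewhere in the plan, a cross-reference in 7.8.2 is enough.

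The cost is wording for one table and a short listing. Local ULNs must be obtained from sites that used a local laboratory, since protocol 5.2.3 speaks only of central reference ranges. The drawback is that laboratories are mixed in one table; the source flag and the local-only count keep that visible. If no local laboratory was used, the count is zero and the matter closes.
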